## 12 Intervention

Participants in the PRINCESS trial will be asked to take an oral dose of probiotic (*Lactobacillus rhamnosus*, LGG and *Bifidobacterium animalis* subsp. *lactis*, BB-12) or a matched placebo once daily for 12 months or until 31/10/18, whichever is sooner. The probiotic or placebo (referred to as Study Product) will be administered by the CHR's normal care giver and provided in capsule form. The preferred route of administration will be in the following order:

- 1) The capsule swallowed whole with water
- 2) The capsule emptied into a small amount of cold or lukewarm liquid and then swallowed
- 3) The capsule opened and its contents sprinkled onto cold or lukewarm food (not hot food) and then eaten

### ***Suitability for religious groups and dietary preferences***

The capsules are suitable for vegans, are Halal and Kosher (Kosher dairy excluding Passover), do not contain any genetically modified organisms or genetically modified raw materials, and allergen labelling is not required. The capsules do contain lactose. Care homes will be provided with documentation detailing the composition of the capsules.

The capsules are stable at room temperature for two years and temperature monitoring is not required for short term (e.g. one month) storage.

### **Labelling and recording**

The capsules will be provided to the care home labelled with a unique pack ID. Packs will be allocated to participants on a monthly basis. The delegated individual (e.g. RN) should enter the participant ID into the online pack allocation system (see section 10.4) and will be allocated a pack ID. The participant ID should then be entered onto the pack label and the CRF completed.

Participants admitted to hospital would not be expected to continue taking the study product during their hospital stay.

### **12.1 Adherence**

Data regarding participant's adherence to the study product will be collected from a number of sources:

- MAR sheets - administration of the study product will be recorded by care home staff using Medication Administration Record sheets (MAR sheets) and monitored by RNs during their visits to each care home. MAR sheet are used in most care homes and will allow incorporation of trial procedures into routine practice easily. If MAR sheets or an equivalent recording system is not used routinely by any care home participating in the PRINCESS trial the research team will provide MAR sheets and training as appropriate.
- Presence of probiotic organisms in bowel - the presence of the probiotic organisms will be assessed in stool samples of participants at baseline, three and up to 12 months. This will give an indication of adherence, survival of the probiotic in the large bowel and potential contamination in the placebo arm.
- Capsule count - regular counts of unused study product will be undertaken by the PRINCESS trial research nurses.

## **13 Adverse Events (Safety)**

### **13.1 General Definitions**

**Adverse Event (AE):** Any untoward medical occurrence in a trial participant which does not necessarily have a causal relationship with this treatment. An AE can therefore be any unfavourable and unintended sign (including abnormal laboratory finding), symptom, or disease.

**Serious Adverse Event (SAE):** Any adverse event that:

- Results in death
- Is life-threatening\*
- Required hospitalisation or prolongation of existing hospitalisation\*\*
- Results in persistent or significant disability or incapacity
- Consists of a congenital anomaly or birth defect
- Other medically important condition \*\*\*

\* Note: The term "life-threatening" in the definition of serious refers to an event in which the participant was at risk of death at the time of the event; it does not refer to an event which hypothetically might have caused death if it were more severe.

\*\* Note: Hospitalisation is defined as an inpatient admission (at least an overnight stay), regardless of the length of stay, even if the hospitalisation is a precautionary measure, for continued observation. Pre-planned hospitalisation e.g. for pre-existing conditions which have not worsened or elective procedures does not constitute an adverse event.

\*\*\* Note: other events that may not result in death are not life-threatening, or do not require hospitalisation may be considered as a serious adverse event when, based upon appropriate medical judgement, the event may jeopardise the participant and may require medical or surgical intervention to prevent one of the outcomes listed above.

An SAE occurring to a research participant should be reported to the main REC where in the opinion of the CI the event was:

- Related – that is, it resulted from administration of any of the research procedures, and
- Unexpected – that is, the type of event is not listed in the protocol as an expected occurrence

### Serious Adverse Reaction (SAR)

For ease of recording and reporting, in this study an SAE thought to be probably or definitely related to the trial/study or intervention (see causality section below) will be referred to as a Serious Adverse Reaction (SAR).

## 13.2 Causality

Causality should be assigned using the definitions in the table below.

For AEs, this assignment should be made by the delegated RN. For SAEs this assignment should be made by the delegated RN and delegated second assessor (e.g. another RN or a clinician involved in the study) and the assessment confirmed by the Chief Investigator or a delegated Clinical Reviewer.

Relationship	Description
Unrelated	There is no evidence of any causal relationship with the trial/study or intervention
Unlikely	There is little evidence to suggest there is a casual relationship (e.g. the event did not occur within a reasonable time after intervention) with the study/trial or intervention. There is another reasonable explanation for the event (e.g. the participant's clinical condition, other treatment).
Possible	There is some evidence to suggest a causal relationship with the trial/study or intervention (e.g. because the event occurs within a reasonable time after intervention). However, the influence of other factors may have contributed to the event (e.g. the participant's clinical condition, other treatments).
Probable	There is evidence to suggest a causal relationship and the influence of other factors is unlikely.
Definite	There is clear evidence to suggest a causal relationship and other possible contributing factors can be ruled out.

### **13.3 Expectedness**

In this study only SARs will be assessed for expectedness by the CI (or delegated Clinical Reviewer).

Based on the manufacturer's information and review of the literature, at the time of writing, any SAR occurring in this study should be classed as unexpected. However, as the manufacturer's safety information is updated every two years and new literature maybe published at any time, when assessing expectedness the CI (or delegated Clinical Reviewer) should refer to the PRINCESS safety reporting management plan as a separate document to the protocol.

#### **Summary of current manufacturer's information**

CHR Hansen's safety and origin information sheet published in March 2015 states that the probiotic strains BB-12 and LGG have been used worldwide since 1985 and 1990 as an ingredient in food and dietary supplements with no reported consumer illness or injury, and that the BB-12 and LGG strains have been tested in more than 140 and 250 clinical studies respectively from new-born pre-term infants to elderly in doses up to at least 100 billion CFU/day with no reported adverse events. Therefore, we do not anticipate any adverse events based on the current manufacturers information.

#### **Summary of current literature**

Based on an extensive review of the literature the CI has concluded that probiotics, including the strains used in PRINCESS, are generally well tolerated by the elderly and the risks to CHR associated with the probiotics used in PRINCESS are very low. A recent paper summarises the current risks (43): Infections (e.g. septicaemia) caused by the probiotic bacteria have not been reported in trials; theoretical risks of gene transfer of antibiotic resistance and over stimulation of the immune response have not been reported; although deleterious metabolic activities e.g. bowel ischemia and D-lactic acidosis in patients with pancreatitis have been reported, the mode of probiotic delivery was different to PRINCESS. Therefore, if any of the above events were to occur in PRINCESS they would be unexpected.

Minor gastrointestinal symptoms such as abdominal cramping, nausea, soft stools, flatulence and taste disturbance have been reported and it is also possible that a minor allergic reaction could occur. If these events were to occur, they would be classed as expected AEs, but would be unexpected if they fulfilled the definition of a SAR.

#### **Summary of current expected events related to the study procedures**

There is a risk of haematoma at the site of venepuncture for a study blood sample; however this would only be expected to be an AE. If the event fulfilled a definition of a SAR, it would be classed as unexpected.

### **13.4 Reporting procedures**

This study is not a CTIMP and the probiotic being used is a well-established food supplement. The study population will have a vast number of health events in the normal course of their care at this stage in their lives. Given the potential frailty of the trial population and the high incidence of hospitalisation and death in the course of routine care, we would aim to not cloud any true emerging safety profile by collection of unrelated data. The following reporting procedure should be used for

PRINCESS. Any queries concerning adverse event reporting should be directed to the PRINCESS Trial Manager in the first instance.

Adverse events will be initially identified either through the PI/Care home staff identifying that an adverse event has occurred and informing the RN/TM, or during routine weekly data collection by the RN.

- **Non-serious Adverse Events** with the causality classification of probably or definitely related to:
  - the study product (such as gastrointestinal symptoms, or ingredient-related allergic reaction)
  - or study procedures (such as a haematoma at the site of venepuncture for a study sample)will be collected as part of routine follow-up (recorded by the RN on the PRINCESS Weekly Record and Weekly Record: Further Information CRF) from the time of consent until the 6 to 12 month follow-up period.
- **Other non-serious AEs** will not be collected. The PI/CHS should manage AEs according to routine care home procedures.
- **All Serious Adverse Events (SAEs)** will be collected as part of routine follow-up (recorded by the RN on the PRINCESS Weekly Record and Weekly Record: Further Information CRF) from the time of consent until the 12 month follow-up period. SAEs will be discussed (in person, by phone or by email) by the RN with a second delegated assessor (e.g. another RN or a clinician involved in the study) to confirm the causality classification (definitely, probably, possibly, unlikely, not related). The details of the second assessment will be recorded on the PRINCESS Weekly Record: Further Information CRF. Where there is a difference in classification between the two assessors, the highest category of causality (most likely to be related) will be selected.
- **Serious Adverse Reaction (SAR):** If the Serious Adverse Event (SAE) is classified as being probably or definitely related to study procedures or the study product (such as septicaemia and the suspected pathogen is identified as either of the strains used in the PRINCESS study product ) it is classed as a **Serious Adverse Reaction (SAR)**. A SAR reporting form should also be completed by the RN and returned directly to the TM (or delegate), or faxed to SEWTU on [name] with a follow up email ([[contact]](mailto:[contact])) within 4 days of the RN becoming aware of the event.

Further information may be required from reviewing the participant's care home records, or reported by care home staff liaising with clinical teams caring for the resident (GP, secondary care).

All SAR reporting forms received by SEWTU will be subject to clinical review by the CI or delegate to confirm causality and assess expectedness.

SEWTU will notify the Sponsor and main REC of all related and unexpected SAEs (i.e. all unexpected SARs) occurring during the trial within **15** calendar days of the CI becoming aware of the event. All

SARs will be reported to the monitoring committees (TMG, TSC and IDMC), sponsor and CHR Hansen (study product manufacturer) as required by the relevant committee/party. All unrelated SAEs will be reported to the TMG and included in the annual report to the IDMC, and any arising safety concerns will also be reported to the main REC as part of the annual progress report.

[figure not shown]

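### Section 13.4 sends SARs and 'unrelated' SAEs to the IDMC; with 'Unrelated' defined in 13.2 as the lowest of five grades, SAEs graded possible or unlikely have no stated route

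*Protocol*

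**What the plan says.** Section 13.2 sets out five causality grades. The lowest, *Unrelated*, reads: "There is no evidence of any causal relationship with the trial/study or intervention". The next, *Unlikely*, is a separate row: "There is little evidence to suggest there is a casual relationship". Above it, *Possible* reads: "There is some evidence to suggest a causal relationship with the trial/study or intervention". *Probable* and *Definite* complete the scale.

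The SAR definition in section 13.1 takes in the top two grades only: "an SAE thought to be probably or definitely related to the trial/study or intervention".

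Section 13.4 has every SAE recorded on the weekly forms and discussed with a second assessor "to confirm the causality classification (definitely, probably, possibly, unlikely, not related"). If the two assessors differ, the grade closer to related is kept. The section then gives two committee routes. For SARs: "SARs will be reported to the monitoring committees (TMG, TSC and IDMC), sponsor and CHR Hansen". For the rest: "All unrelated SAEs will be reported to the TMG and included in the annual report to the IDMC".

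Section 22.2 gives the data monitoring committee a general remit over patient safety and data quality. It does not say which SAEs the committee receives.

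**The concern.** The two routes in 13.4 do not cover the scale in 13.2 if *unrelated* carries its defined meaning. The grades left out are the middle ones.

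Those grades matter in this population. Under 13.2, *Probable* requires that the influence of other factors is unlikely, while *Possible* is used when the participant's condition or other treatment may have contributed. For frail care home residents another contributing factor can nearly always be offered. A harm that nobody has yet recognised would therefore tend to be graded *Possible* or *Unlikely*. A committee looks for such a harm by reviewing all SAEs, whatever individual assessors concluded. If staff applied the sentence literally, the IDMC's annual report would omit the SAEs whose cause is least certain.

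**Working it through.** There is no figure to reproduce. The check matches each causality grade in 13.2 to the committee routes in 13.4.

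| Grade (13.2) | SAR under 13.1? | Stated route to the IDMC (13.4, literal reading) |
|---|---|---|
| Definite | yes | as a SAR |
| Probable | yes | as a SAR |
| Possible | no | none stated |
| Unlikely | no | none stated |
| Unrelated | no | annual report, and the TMG |

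Three of the five grades have a route and two do not (5 − 3 = 2).

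**Is there another route in the text?** Sections 13.1 and 13.3, the front-page SAE instructions and section 22.2 were read for one. Section 13.1 covers reports to the ethics committee of events that are related and unexpected. Section 13.3 covers expectedness of SARs. The front-page instructions cover the forms and SARs. Section 22.2 states a remit. None names possible or unlikely SAEs, or SAEs other than SARs in general, as going to the IDMC.

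**Effect of the disagreement rule.** Suppose one assessor grades an SAE *Unrelated* and the other *Possible*. Section 13.4 keeps *Possible*. Had both chosen *Unrelated*, the event would be in the annual report. Read literally, raising the suspicion takes it out, so a cautious rule works against its purpose.

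**The alternative reading.** Section 13.4 describes the events notified to the sponsor and ethics committee as "all related and unexpected SAEs (i.e. all unexpected SARs) occurring during the trial". That equates related with SAR. If *unrelated* is its complement, it covers *Possible*, *Unlikely* and *Unrelated*, and all five grades reach the IDMC. But an SAE that 13.2 says has some evidence of causality would then carry a word that 13.2 defines as no evidence.

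So the literal reading leaves a gap in the routing, and the alternative leaves a contradiction in terms. The same edit removes both.

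**The case against.** The strongest reply is that 13.4 uses related and unrelated as a pair. It equates related with SAR just before the sentence in question. Section 13.1 also uses related as a yes-or-no term for ethics committee reporting. When 13.4 lists the five grades, it calls the lowest one not related, so within that section *unrelated* is not the grade label. This is a plausible account of what the authors meant, and on it no SAE is withheld. It stands as an account of intent. It does not rescue the wording, because 13.2 defines *Unrelated* by name, and staff who follow a written procedure will look to that definition.

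The SAE flowchart is not shown, and the separate safety reporting management plan and the committee charter are not at hand. Any of these might state a fuller route, so the gap is established only for the visible text of the protocol. That limit stands.

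The protocol also has safeguards. Section 13.4 collects SAEs of every grade. Section 13.2 has the Chief Investigator or a delegated reviewer confirm causality for all SAEs, and section 21 puts the Chief Investigator at the head of the TMG. Deaths and hospital stays are secondary outcomes compared between arms regardless of causality (sections 5.1 and 18.2). These safeguards stand, and they limit the point to what the committees are sent.

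A reader might infer that the trial's SAE totals by arm would be incomplete, or that a sizeable number of SAEs would be hidden from the IDMC. The protocol supports neither inference. The data are collected whatever the grade. A count would need the share of SAEs graded possible or unlikely, which the protocol does not give. The 250 days in section 17.2 cannot supply the follow-up time either, because they describe days with antibiotic data and not SAE observation. The admission figures in section 4.2 are not limited to admissions that meet the SAE definition.

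**Conclusion.** The point holds as a wording defect in a safety-reporting sentence. With 13.2's definition of *Unrelated*, two of the five causality grades have no stated route to the TMG or the annual IDMC report. With the wider meaning that 13.4 hints at, every grade is routed but the term contradicts 13.2. The text should be corrected whichever was meant.

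The conclusion rests on the protocol text alone and assumes that neither the flowchart nor the safety reporting management plan already states a complete route. It does not show that the sponsor chose to withhold these events or that any were withheld. No number of affected SAEs can be given. The effect is limited to committee reporting; data collection, sample size, power and the primary analysis are unaffected. The correction is still worth making, because it costs almost nothing and concerns what the safety committee sees.

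**What to change.** In section 13.4, replace the words 'All unrelated SAEs' with 'All SAEs not classified as SARs (possible, unlikely and unrelated)'. Bring the flowchart and the safety reporting management plan into line if they use the same term. The layout of the tables can be left to the IDMC charter.

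The cost is one phrase and perhaps a slightly longer committee listing. All SAEs are already recorded and graded, so no new data are needed. The protocol ends routine recording by 31/10/2018 and this version is dated 15/04/2019, so it is also worth confirming that the annual reports already sent included the possible and unlikely SAEs. If they did not, a complete listing can go to the committee with the results, which section 23 has it see before publication.

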**Contact details for reporting SARs**

**Please Fax to [name], attention Princess Trial Manager.**

**Queries**

**[contact] (Mon to Fri 09.00 – 17.00)**

**SAE Flowchart**

## 14 Adverse Events (Human Tissue)

### 14.1 General Definitions:

**(Human Tissue) Adverse Event:** Any untoward occurrence associated with the procurement, testing, processing, storage and distribution of relevant material and cells that might lead to loss or damage of relevant material or breach procedures protecting the donor and/or relevant material.

Where **Relevant Material** means any material, other than gametes, removed from the body which consists of or includes human cells. In the Human Tissue Act references to relevant material from a human body do not include:

- embryos outside the human body,
- hair and nail from the body of a living person,
- cell lines or any other human material created outside the human body,
- serum, plasma, DNA and RNA,

### 14.2 PRINCESS Reporting Procedures:

Any Human Tissue Adverse Event thought to be related to the stool, blood or saliva samples (such as sample being taken without consent, an incorrectly labelled or lost sample, or spillage during transport) will be collected as part of routine follow-up (recorded by the RN on the PRINCESS Weekly Record and Weekly Record: Further Information CRF and monitored by SEWTU) from the time of consent until the 12 month follow-up period.

SEWTU will notify the Sponsor of all human tissue adverse events occurring during the trial, and all other requirements as specified by the Human Tissue Act.

## 15 Trial procedures

### 15.1 Location

All trial appointments will take place at the care home where the participant is resident. All trial procedures will be carried out by either the participants' normal care providers or by RNs.

### 15.2 Data collection/assessment

Eligible participants or their consultee will have an appointment arranged at which informed consent or a consultee declaration (see section 10.3) will be obtained. A second baseline appointment will be made, at which baseline samples will be taken, and baseline data recorded.

The follow-up schedule will depend on the length of time that a participant has been in the study.

Where possible, participants will have a baseline assessment, and three- and 12-month follow-ups (participants randomised pre-December 2017).

Due to time limitations, some participants may have a truncated follow-up and will receive either a baseline assessment and 3 month follow-up (those randomised in May 2018), or a baseline

assessment, 3 month follow-up and a second follow-up between 6-10 months post-randomisation (those randomised between December 2017 and April 2018).

The target window for the 3-month follow-up is -2/+4 weeks.

The target window for the 12-month follow-up is 11 months +/- 1 month.

Infection, antibiotic use, adverse events and study product use will also be recorded by the RN from care home notes at regular intervals using the weekly record forms for 12 months post randomisation or until 31/10/18, whichever is sooner.

A sub-set of patients who have been taking the study product for a minimum of two months and who have had an influenza vaccination after the two month period will have an appointment arranged to attend a third appointment about four weeks (28 days) after the influenza vaccine.

Influenza vaccinations will be administered via routine care. The date of administration will be recorded.

